2.1 – Our primary hypothesis is that, after reaching bilirubin levels > 2 mg/dL, patients receiving Omegaven® will reach a bilirubin level ≤ 2 mg/dL faster than patients receiving conventional fat emulsions. Additionally, while patients receiving Omegaven™ will experience a decrease in their levels of bilirubin and other hepatic enzymes over time, patients receiving conventional emulsions will maintain high levels of bilirubin and other hepatic enzymes over time.

2.2 – Patients with surgical gastrointestinal disease and cholestasis will have better clinical hepatic outcomes than patients receiving conventional emulsions.

2.3 – Since patients receiving Omegaven® will have improved immune function, they will have a lower infection rate than patients receiving conventional fat emulsions.

2.4 – Due to a better general hepatic condition, patients receiving Omegaven® will also experience lower occurrence of liver transplant, death from hepatic associated causes, and blood transfusions.

2. Background and Significance

Parenteral Nutrition Associated Liver Disease (PNALD)

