Assessment of the effect of treatment will be based on a non-randomized, open-labeled, prospective study of intravenously administered Omegaven[®] fat emulsion to determine safety and preliminary efficacy in the treatment of PN associated liver injury. This treatment group will be compared to a group based on historical controls, i.e., a subset of patients (those whose direct bilirubin levels was ever > 2 mg/dL) previously studied by Andorsky et al.(31) This study included neonates treated between 1986 and 1996 who depended on parenteral nutrition for at least 90 days after surgical therapy for congenital or acquired intestinal diseases. Our study will primarily follow the patients included in Andorsky et al. study from 2 months before direct bilirubin first reached a level > 2 mg/dL (baseline date) until 2 months after patients either reached 3 consecutive bilirubin levels \leq 2 mg/dL or reached one bilirubin level \leq 2 mg/dL and were weaned from PN died, or underwent a liver transplant. In our exploratory analyses, we will include the entire available follow-up time in Andorsky et al. dataset for each patient.

b. Patient Selection and Inclusion/Exclusion Criteria

Omega-3 Fat Emulsion (Omegaven[®])

After the diagnosis of PNALD is made, patients who are followed by the Clinical Nutrition Service (CNS) or General Surgery Program, in conjunction with the patient's primary physician, will contact [name] or [name] and an evaluation will be performed. Cases may also include referrals of patients with PNALD from other healthcare facilities or self-referrals. If the patient's parents or guardians agree to participate in the study, informed consent will be obtained. The history of present illness and past medical history will be reviewed with the guardian and pertinent demographic and medical information will be recorded on data collection forms. This form will be used to record all laboratory results, nutritional history, and descriptions of any liver biopsies performed.

Though most patients receiving parenteral nutrition do not develop end stage liver disease, there is a small percentage of patients, typically infants and children on prolonged courses of parenteral nutrition, who do go on to develop fulminate liver failure. The study population of this protocol is limited to patients felt to fulfill any one of the following conditions:

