As previously mentioned, Omegaven® may be infused in the same manner as conventional fat emulsions through either a central or peripheral line. The emulsion is isotonic. It is compatible with parenteral nutrition solutions and may be co-infused via y-site. Per Infection Control, source containers must be changed every 12 hours and unused product discarded. Omegaven® may be infused through a 1.2micron inline filter.

Dose Modification

Lipid Intolerance

If lipid intolerance develops, defined as serum triglyceride levels > 200 mg/dL, the following will be considered prior to reducing the dose:

- a) If the level was obtained while the patient was receiving a continuous 24-hour infusion of Omegaven®, the total dose should be infused over 20 hours, and a repeat serum triglyceride level obtained prior to resuming the infusion 4 hours later.

b) Other sources of lipid intolerance should be considered and addressed (drugs, renal disease)

If the triglycerides continue to remain high despite the aforementioned interventions, a dosage reduction of 25% of the current dose will be considered.

High Glucose Infusion Rate

Subjects with a high glucose infusion rate (GIR) will have a dose increase up to 1.5 grams/kg/day to allow for a reduction in PN calories from carbohydrates at the discretion of the Omegaven study team and the nutrition service.

Duration of Therapy

Patients will remain on Omegaven® until weaned from PN. Patients may continue monotherapy with Omegaven® as an additional source of calories after the dextrose/protein portion of PN is discontinued

In the event that a patient who has been listed for a liver or liver/intestinal transplant has an organ become available, the participation in this protocol will not preclude them from receiving the transplant.

Disruption of Therapy

In event that Omegaven® cannot be administered (i.e. loss of central venous catheter access, fluid restrictions, need to administer an incompatible medication/blood product), the infusion of Omegaven® may be interrupted and resumed when the conflicting situation is resolved. Some potential interventions that can be used include:

Situation	Possible Solution
Loss of central venous access	Administer via peripheral route
Fluid restriction	Consult with pharmacy to concentrate PN, medications to allow for administration

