Limited access, need to administer incompatible medications	Stop Omegaven® infusion, flush catheter with either NS or dextrose, administer incompatible medication, flush catheter, resume infusion; may be necessary to infuse Omegaven® over 8 -24 hours. Multiple syringes should be used so as to keep maximum hang time of Omegaven® source container less than 12 hours) Regardless of the infusion time, the infusion rate cannot exceed 0.15g/kg/hour.

Discontinuation of Therapy

Patients will continue to be followed by the Center for Advanced Intestinal Rehabilitation (CAIR) Program upon discontinuation of therapy with Omegaven® for a minimum of 2 months after the treatment is stopped.

Resumption of Therapy

For patients who have been off the protocol more than 1 year, in the event that the patient must receive intravenous fat emulsion, treatment with Omegaven® will resume only if the patient shows evidence of PN liver damage (elevations in direct bilirubin ≥ 2 or pathology findings consistent with cholestasis). Otherwise, the patient will be treated with conventional fat emulsion.

Soybean based Fat Emulsion (Intralipid® and/or Liposyn®)

Subjects in the Andorsky et al cohort received one of two commercially available intravenous fat emulsions (IFE), Liposyn® II or Intralipid®. IFE is provided as an oil-in-water emulsion derived from egg phospholipids, soybean or safflower oils and glycerol. Although three concentrations are commercially available (10, 20, 30%) only the 10 and 20% concentrations have been approved for use in children. Both Liposyn® II and Intralipid® contain soybean oils. Table 1 summarizes the composition of both products.

Details of IFE Administration

Regardless of the product used, doses less than 96 ml/day were repacked into syringes to allow for administration via syringe pump. Doses greater than 96ml/day were dispensed in the original manufacturer's container. If patients were discharged home on either IFE, all doses were administered from the original manufacturer's container.

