Generally, primary safety analyses will be based on time from baseline or 30 days after baseline until two months after patients first reached direct bilirubin levels $< 2\text{mg/dL}$. Baseline will be defined as information collected at the date that treatment starts for Omegaven[®] patients and on the date that patient reached bilirubin levels > 2 for soybean oil fat emulsion patients. Information on mortality and transplant will be collected during the whole treatment with Omegaven[®] and during the whole period for which we have data available in the Andorsky et al. dataset. Primary efficacy analysis will include time from baseline until the patient normalizes bilirubin (presents three consecutive direct bilirubin $\leq 2\text{ mg/dL}$ or a direct bilirubin $\leq 2\text{ mg/dL}$ and weaned from TPN). With exploratory purpose, we will also describe the curve of the several markers for the entire period that Andorsky et al. recorded data.

Outcome/Endpoints

1. Treatment safety

Our primary outcome for treatment safety will be based on patient's essential fatty acid profile. We will compare patients before treatment with Omegaven[®] started and after treatment started (one month after treatment started until treatment stopped) with respect to the frequency with which triene/tetraene ratio > 0.2 at any time. We will also compare the occurrence any event of of hypertriglyceridemia (serum triglyceride $> 400\text{mg/dL}$) between Omegaven[®] and soybean oil fat emulsions. Primary analyses for these and all other safety outcomes will be based on a follow-up time for Omegaven[®] and soybean oil fat emulsions starting 30 days after baseline, i.e., 30 days after treatment started for Omegaven[®] patients and 2 months after the first direct bilirubin level $< 2\text{ mg/dL}$ was recorded. We will also explore comparisons including the time from baseline until the end of follow-up period.

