Data will be collected by the PI (MP), the managing co-investigator (KG), and the clinical coordinator with the assistance of the nursing unit liaisons and research assistants in [name] laboratory. Hospital charts will be reviewed for pertinent clinical information. Results of liver biopsies and blood chemistries will be obtained from PowerChart within the Cerner computer system at CHB. Specifically, the history of present illness, past medical history, and birth history, pertinent physical exam findings including patient weight, the results of liver biopsies, and parenteral and enteral feeding history will be collected. The information will be recorded on hard copy data collection forms.

Soybean based Fat Emulsion (Intralipid® and/or Liposyn®)

Data will be extracted from the Excel spread sheet used to store data of the Andorsky et al. study. Additionally, we will obtain information about date of birth (to estimate age at each visit and nutritional safety outcomes) and blood transfusions in Power Chart within the Cerner computer system at CHB. In the original study performed by Andorsky et al., data was abstracted from charts, nursing flowsheets (for nutritional intake data), and outpatient visit notes in two week intervals.

g. Study Timeline (as applicable)

This study will end when the results of an FDA approved clinical trial proves Omegaven® treatment to be ineffective or the product is approved for use in the United States. The investigators proposal to the Orphan Products Grants Program of FDA submitted in spring 2007 which was accepted.

h. Adverse Event Criteria and Reporting Procedures

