We will also describe individual profiles over time (i.e., 2 months before baseline or birth until end of follow-up period) for all subjects using graphical methods. Trends in liver function markers over time will be explored using generalized linear models in which correlations of observations within subjects will be accounted using a generalized equations or random effects approach. In these models we will hypothesize that for both groups biochemical levels increase for all tests with equal slope before treatment. After treatment, however, levels should be decreasing for patients in the Omegaven® group. We will perform these analyses including only subjects who did not die or undergo transplantation and including all subjects but assigning for subjects who died or underwent a transplant their worse possible outcome after they died or had the transplant. Using descriptive statistics, we will also explore the association between spikes in blood tests over time and predictors including transfusions of red blood cell products and blood stream infections.

Assessment of efficacy will be also based on comparison of means (or medians) of the mean and maximum modified PELD scores of each subject across all follow-up weeks. Adjustments of these comparisons for potential confounders will be based on linear regression models. Mean rates of infection will be compared using logrank and Cox proportional hazards models. Proportions of liver transplant, mortality, and red blood cell product transfusion events between the two groups will be compared via Fisher's exact test (or Chi-square tests, when appropriate). Adjustments for potential confounders will be considered using exact stratified analysis and logistic regression models.

Missing Values

Since data will be prospectively collected in the Omegaven® group, we anticipate that data will be nearly complete, particularly for the safety outcomes. In both groups, we will explore imputing any laboratory values that are missing up to two visits in the middle of the follow-up period using linear or non-linear interpolation, as appropriate. To interpolate direct and total bilirubin, we will primarily use the two closest observations, since bilirubin could be very different in points in time located further apart from the missing observation. We will compare conclusions of analyses based on imputed values with analyses based on the available information.

Potential Study Limitations

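### The modified PELD comparison sets no common follow-up window or measurement grid, so maximum scores can differ between groups with no difference in PELD at any given week, in an uncertain direction

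*Combined protocol and SAP*

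**What the plan says.** Section 5c (Analysis of Efficacy) compares group means or medians of the "mean and maximum modified PELD scores of each subject across all follow-up weeks". The only adjustment named is linear regression for potential confounders. The baseline predictors listed in section 4d include neither length of follow-up nor number of measurements.

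Other sections bear on what the follow-up weeks are:

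- **Section 4, study design, first historical cohort.** Primary follow-up runs "until 2 months after patients either reached 3 consecutive bilirubin levels" at or below 2 mg/dL. One such level with weaning from PN, death or transplant also ends it.
- **Section 4e.** "Primary efficacy analysis will include time from baseline until the patient normalizes bilirubin". The longer record is for exploration only: "we will also describe the curve of the several markers for the entire period" recorded in that cohort.
- **Section 4d, Omegaven patients.** "Patients will remain on Omegaven® until weaned from PN", and they are then followed "for a minimum of 2 months after the treatment is stopped".

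The measurement intervals also differ. Section 4f says the control data came from charts, nursing flowsheets and "outpatient visit notes in two week intervals". The lab schedule in section 5f asks for weekly panels in Omegaven patients while direct bilirubin is above 2 mg/dL. Table 2 has coagulation labs weekly until bilirubin is below 2 mg/dL and monthly afterwards.

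I found no definition of modified PELD, and no end of follow-up or recording interval for the 1999-2004 control cohort.

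**The concern.** A maximum cannot fall when a window is lengthened or more measurements are added to it. If one group is followed longer or sampled more finely, its expected maximum is higher even when the two groups have the same PELD distribution every week. Regression on baseline confounders does not remove this, and the limitations in section 5c do not mention it.

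The length of the window is also tied to the primary outcome. Hypothesis 2.1 expects Omegaven patients to normalize "faster than patients receiving conventional fat emulsions". On the normalization-based windows, controls would then be followed longer, and part of a PELD difference would restate the bilirubin result while looking like separate evidence.

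**Working it through.** The plan gives no SD, expected difference, sample size or power for PELD, so there is no figure to reproduce. The check asks how large a difference appears when there is none.

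**Inputs from the documents.** Controls every 2 weeks (4f); Omegaven weekly while bilirubin is above 2 mg/dL (5f, Table 2); 20 or 30 patients per group and alpha 0.05, borrowed from the safety power tables for illustration.

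**Assumptions.** Window lengths; weekly correlation rho of 0 to 0.8; within-patient SD 1; between-patient SD 1 or 2; Omegaven sampling weekly throughout its window.

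**Formulas.** With interval s and window W, the number of measurements is k = W/s + 1. For independent values, E[max] = ∫ x·k·φ(x)·Φ(x)^(k-1) dx. For correlated values I simulated x(t) = rho·x(t-1) + √(1-rho²)·e(t), with the same process in both groups.

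**Step 1: maximum, documented intervals.** Control minus Omegaven, in within-patient SD:

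| Window, Omegaven vs control (weeks) | k | rho 0 | rho 0.5 | rho 0.8 |
|---|---|---|---|---|
| 12 vs 12 | 13 vs 7 | 1.36-1.66 = -0.30 | 1.28-1.51 = -0.23 | 1.05-1.17 = -0.12 |
| 12 vs 24 | 13 vs 13 | 1.67-1.66 = 0.01 | 1.62-1.51 = 0.11 | 1.40-1.17 = 0.23 |
| 16 vs 32 | 17 vs 17 | 0.00 | 0.10 | 0.22 |
| 12 vs 36 | 13 vs 19 | 1.85-1.66 = 0.19 | 1.80-1.51 = 0.29 | 1.61-1.17 = 0.44 |
| 8 vs 24 | 9 vs 13 | 0.19 | 0.32 | 0.43 |
| 8 vs 52 | 9 vs 27 | 0.51 | 0.66 | 0.83 |

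If both groups were weekly, 12 vs 36 weeks would give 2.13-1.66 = 0.47 (rho 0) to 1.76-1.17 = 0.59 (rho 0.8). The coarser control grid removes part of the excess.

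**Step 2: the windows the other way round.** If Omegaven patients count to weaning plus 2 months and have the longer window, say 36 weeks against 12, the difference is 1.36-2.13 = -0.77 (rho 0) or 1.05-1.76 = -0.71 (rho 0.8).

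**Step 3: false-positive rate** of a two-sided 5% t-test on the maximum, rho 0.5 to 0.8, documented intervals:

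| Windows (weeks) | Between-patient SD | n = 20 | n = 30 |
|---|---|---|---|
| 12 vs 36 | 1 | 11-20% | 15-27% |
| 12 vs 36 | 2 | 8-9% | 8-12% |
| 12 vs 24 | 1 | 6-9% | 7-11% |
| 12 vs 24 | 2 | 5-7% | 6-7% |

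**Step 4: falling scores.** Let both groups fall from 3 SD to 0 over 12 weeks, both measured weekly. The expected maximum over 12 vs 52 weeks is 3.79 vs 3.80 (rho 0) and 3.33 vs 3.36 (rho 0.8). The peak lies near baseline, so window length adds almost nothing.

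**Step 5: the mean.** In every stationary scenario the expected mean is 0 in both groups, so the number of measurements does not bias it. Now let the score fall linearly from 3 SD to 0 at normalization and stay flat for 8 weeks, measured weekly. Normalizing at 12 weeks gives 3 × 6.5 / 21 = 0.93. Normalizing at 36 weeks gives 3 × 18.5 / 45 = 1.23. Over a common 0-20 week window the slower path averages 3 × (21 - 210/36) / 21 = 2.17 against 0.93. The subject-specific mean thus partly restates speed of normalization, and here it understates the real gap because the slow path is averaged over more weeks.

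**Step 6: common window and grid.** With 12 weeks at 2-week intervals in both groups, the expected maximum at rho 0.8 is 1.05 in each, the difference is 0, and the test returns to 5%.

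**The case against.** The stationary score is the assumption most favourable to the concern. Section 5c expects levels to fall after Omegaven starts, and step 4 shows that window length then hardly affects the maximum. That stands, although a coarser grid in one group still lowers that group's maximum.

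Three stronger readings are tempting, and the documents support none of them:

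- **Controls are measured more often.** They were abstracted every 2 weeks against weekly Omegaven panels. They have more measurements only if followed more than about twice as long.
- **The bias is known to favour Omegaven.** The stopping rule at normalization plus 2 months is written for the first control cohort. Omegaven patients are treated to weaning and followed at least 2 months more, so they could have the longer window. Section 4d also expects Omegaven patients to be sicker at baseline. Early death or transplant shortens follow-up, and no rule for this PELD summary is stated.
- **Any PELD difference would be artefact.** A group that normalizes more slowly may truly reach higher scores.

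Section 5c does plan longitudinal models of liver markers, with analyses for death and transplant, but PELD is not named there. The outcome list in section 4e breaks off after the safety items, so a PELD definition may have been lost from the text. PELD is an additional analysis in a study seeking preliminary evidence, and the primary time-to-normalization analysis is unaffected.

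**Conclusion.** The point holds as a gap in specification. The plan compares a maximum and a mean over windows that are undefined and can differ between groups, on grids that do differ, with no correction for either. For a stationary score with weekly correlation 0 to 0.8, and controls followed as long as or longer than Omegaven patients, the artefact in the maximum is about -0.3 SD at equal 12-week windows, 0 to 0.4 SD for moderately unequal windows and 0.5 to 0.8 SD for 8 vs 52 weeks. The window-length part is near zero if scores fall equally from baseline, and the sign turns negative if Omegaven patients have the longer window. All window lengths, correlations and SDs are assumptions, so neither size nor direction can be fixed from the documents. The mean has no measurement-count bias, but it is hard to interpret because it averages over different disease periods. This is a modest point on a supporting analysis.

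**What to change.** In section 5c, define the PELD comparison over one fixed period from baseline on the same grid in both groups, for example by thinning Omegaven values to 2-week intervals. Analyse it with a mixed model adjusted for baseline PELD, or compare a time-standardised area under the curve or maximum over that common window. A common window without a common grid is not enough, as the 12 vs 12 week row shows. Apply to PELD the two analyses for death and transplant that section 5c already gives for marker trends: assigning the worst outcome, and excluding those patients. State the definition of modified PELD and the control cohort used.

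The cost is a change of analysis-plan wording, with no new procedures. The downside is that later PELD values drop out of this comparison and some patients may lack values late in the window, particularly once Omegaven coagulation labs become monthly. The mixed model copes with such gaps better than a maximum does.

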Additional comparisons across treatment periods for subjects receiving Omegaven® will be aimed to assess occurrence of spontaneous bleeding (e.g., unexplained bruising, oozing from gums/incision sites), and maximum triene/tetraene ratio, minimum platelets, and maximum international normalized ratio (INR), trends in pre-albumin (age standardized levels). We will also explore trends in coagulopathies based on curves of platelets, prothrombin time (PT), partial thromboplastin time (PTT) over time, and INR. We will also describe the rate with which INR ratios were > 2 (number of days/follow-up time), as a marker of coagulopathies.

Additional comparisons between Omegaven® and soybean oil fat emulsion groups will be performed with regards to rate in which albumin is > 3 g/dL, maximum triglyceride level, rate of blood stream infections (number of positive blood cultures/follow-up-time under PN after baseline), rate of central venous catheter (CVC) infections (number of CVC infections/follow-up time and number of gram positive CVC infections/follow-up time), and occurrence of anaphylactic reactions after baseline.

Nutritional outcomes between Omegaven® and soybean oil fat emulsion groups that will be compared include changes in weight- and height-for-age Z-scores from baseline to 10% PN or cessation of PN..

We will describe trends over time for all outcomes associated with fatty acid profiles (including triene/tetraene ratios, triglycerides, total omega-6 fatty acids, total omega-3 fatty acids, total saturated, total monounsaturated, and total polysaturated fatty acids). Specific fatty acids such as arachidonic, palmoleic, palmitic, oleic, stearic, and linoleic fatty acids will also be evaluated and described. Also, for exploratory purposes, we will compare the trend in weight- and height-for-age Z-scores between both groups.

2. Omegaven®

3. The patient will complete treatment with Omegaven® in this study when he/she is completely off PN, develops a contraindication for further use, or the patient/family requests to be removed from the study.

f. Data Collection Methods, Assessments and Schedule

Omega-3 Fat Emulsion (Omegaven™)

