Primary outcomes measured only in the Omegaven® group will include whether the triene/tetraene ratio was ever > 0.2 during the intervention period and whether the INR was ever > 2. Secondary outcomes measured only on the Omegaven® group will include platelets, prothrombin time (PT), partial thromboplastin time (PTT), and other components of the fatty acid profile. Analysis of all categorical outcomes will be based on proportions and of all continuous outcomes will be based on means or medians of the individual mean, maximum or minimum values, as appropriate, during the respective follow-up period. Comparisons between periods (pre and post-treatment) will be performed based on paired tests, parametric or non-parametric, as appropriate. We will also explore trends over time (e.g., decreasing for INR and increasing for pre-albumin) and estimate p-values via regression models using generalized estimating equations or random effects to account for within subject correlations. When describing outcomes over time, we will explore the effect of predictors of poor hepatic outcomes, such as use of antifungal agents (e.g., amphotericin) and antidiarrheal agents (e.g., loperamide), on potential spikes.

Primary outcomes measured in the Omegaven® and soybean based fat emulsion groups will include whether triglycerides were ever > 400mg/dL, whether albumin was ever > 3, any occurrence of unexpected bleeding and number of times it occurred, occurrence of any anaphylactic reaction, rate of blood stream infections as shown by positive blood cultures, rate of line infections and gram positive central venous catheter infections. Outcomes will be summarized for each study group based proportions, poisson rates, mean, minimum, or maximum over the subject follow-up period, and statistical significance of differences between groups will be estimated with exploratory purpose via Fisher's exact test, Wilcoxon or t-tests, as appropriate.

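### Infection is defined as a count per follow-up time, but the efficacy section compares it with first-event methods, and the plan does not say which infection test governs

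*Combined protocol and SAP*

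**What the plan says.** - **Specific Aims, hypothesis 2.3.** Because of improved immune function, patients on Omegaven are expected to do better on infection: "they will have a lower infection rate than patients receiving conventional fat emulsions".
- **Definition of Primary and Secondary Outcomes/Endpoints.** The blood stream endpoint is a count over exposure: "number of positive blood cultures/follow-up-time under PN after baseline". Central venous catheter (CVC) infections are built the same way: "number of CVC infections/follow-up time and number of gram positive CVC infections/follow-up time".
- **Data Analysis Plan, Analysis of Safety and Tolerability.** Blood stream and line infection rates stand in a mixed list of outcomes measured in both groups. The summaries are "Outcomes will be summarized for each study group based proportions, poisson rates, mean, minimum, or maximum over the subject follow-up period". For testing, "statistical significance of differences between groups will be estimated with exploratory purpose via Fisher's exact test, Wilcoxon or t-tests, as appropriate". The same section makes the primary safety analyses descriptive.
- **Data Analysis Plan, Analysis of Efficacy.** "Mean rates of infection will be compared using logrank and Cox proportional hazards models". No counting-process layout, recurrent-event extension or robust variance is mentioned.

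No section names a regression model for the rate, says how a second or third infection enters the log-rank or Cox analysis, or ranks the two families of tests.

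**The concern.** A rate and a first-event hazard are different quantities. Two groups can have the same proportion infected, at the same times, and yet differ several-fold in infections per month. If the plan reports infections per unit of PN time and attaches a log-rank p-value, the p-value does not belong to the reported figure.

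The point has some weight here for two reasons. First, follow-up is unequal by design: the safety window closes two months after bilirubin falls, and the primary hypothesis is that this happens sooner on Omegaven. Second, the comparison is non-randomised and the plan expects to adjust for baseline predictors. Cox is the only adjusted method named for infection, and it does not adjust the rate.

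**Working it through.** **Nearest stated figure.** The plan gives no infection rate, rate ratio, dispersion or power for infection, so there is no figure on this point to reproduce. The closest is Table 5 (Fisher's test, 20, 25 or 30 per group, alpha 0.05). Exact enumeration of the two-sided test reproduces all 18 cells to within about 0.4 percentage points. Those cells concern a yes/no event and say nothing about a rate.

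**A worked contrast (invented data).** Take 25 patients per group, each followed for 6 months, with 15 infected in each group. Each infected child has 1 infection in one group and 4 in the other.
- Rates: 15/(25 × 6) = 0.10 per month and 60/(25 × 6) = 0.40 per month, a ratio of 0.25.
- Fisher on any/none (15 of 25 v 15 of 25): p = 1.0.
- Wilcoxon on each child's count/time: p = 0.02. t-test on the same quantity: p < 0.001.
- Log-rank sees only the first infections. If these fell at the same times in both groups, it would show no difference.

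**How much a first-event analysis drops.** With mean count μ per patient and gamma frailty variance θ, the chance of at least one infection is 1 − (1 + θμ)^(−1/θ). At an assumed 0.3 infections per month over 6 months, rate ratio 0.5 and θ = 0.5:
- control: μ = 1.8, chance = 1 − 1.9⁻² = 0.723
- treated: μ = 0.9, chance = 1 − 1.45⁻² = 0.524
- share kept = (0.723 + 0.524)/(1.8 + 0.9) = 0.46

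Simulation with follow-up varying between patients gave 43% kept, so 57% dropped.

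**Power by simulation, two-sided 5%.** Infection rates, rate ratios, dispersion and follow-up are assumptions; group sizes are taken from the plan's power tables. The rate model is negative binomial in the first two rows and a rate ratio with robust variance in the others.

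| Assumed scenario | Log-rank, first infection | Rate model | Infections dropped |
|---|---|---|---|
| 1/year, rate ratio 0.6, 30 per group | 16-21% | 22-28% | 31-38% |
| 3/year, rate ratio 0.6, 30 per group, 0.3-1.2 years at risk, dispersion 0.3-1.0 | 18-31% | 35-56% | 59-69% |
| 0.1/month, rate ratio 0.5, 25 per group, mean 6 months, frailty variance 0.5 | 23% | 26% | 31% |
| 0.3/month, otherwise as the row above | 34% | 55% | 57% |
| 0.3/month, frailty variance 0 | 50% | 77% | 51% |

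Across all scenarios run, including those with no true difference, 31% to 72% of infections were dropped.

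**Tests on each patient's count/time.** In the 3/year scenario at dispersion 0.3, Wilcoxon had 45% power, the t-test 48% and negative binomial 54%. At dispersion 1.0 the figures were 27%, 31% and 35%. The t-test is thus within about 4 to 6 points of the model.

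**Type I error (equal true rates, 25 per group).** Log-rank 5-6%; Wilcoxon and t on patient rates 4-7%; rate ratio with robust variance 5-7%. Fisher on any/none rose to 15% when mean follow-up was 12 v 6 months. Plain Poisson reached 16% at frailty variance 0.5 with equal follow-up, and 23% with 12 v 6 months.

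**The case against.** The strongest reply has four parts.

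1. *The safety tests are not at fault in the same way.* This stands. A reader might infer that every listed test discards repeats. Wilcoxon and t-tests can be applied to each patient's count divided by time, exactly as the endpoint is defined; they then compare rates and keep every infection. Their limits are that a short and a long follow-up get equal weight and that they are unadjusted.

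2. *Fisher is not assigned to infection.* This also stands. The safety section gives one menu of tests for a mixed list in which several outcomes are yes/no. Fisher suits those. The documents do not support saying that it will be used for infection rates, only that nothing rules it out.

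3. *The context is modest.* Poisson rates are among the planned summaries, primary safety analyses are descriptive, the safety tests are exploratory, and the primary efficacy outcome is time to bilirubin normalisation. So there is no contradiction within a primary test. The efficacy comparison of infection, however, carries no exploratory label and serves a numbered hypothesis.

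4. *The size depends on an assumed infection rate.* True. At about one infection per year the power gap is small and most infections are kept. The mismatch between the reported rate and the tested hazard does not depend on that rate. Cox can also be extended to recurrent events, but the plan does not say that it will be.

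**Conclusion.** The point holds for the efficacy section. Its named methods, as ordinarily applied, test the hazard of a first infection, whereas the hypothesis and the endpoint concern a rate that counts repeats. The relation to the exploratory tests in the safety section is not stated.

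The demonstrated cost is a mismatch of quantity and a loss of efficiency: from about 3 points of power at low infection rates to more than 20 at higher ones. It is not an inflated false-positive rate, since log-rank kept close to 5%. A reader might also infer that most infections would be thrown away. The documents give no infection rate, and the share dropped ran from 31% to 72% depending on the one assumed.

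A related gap is the efficacy rule that gives an infinite event time to patients who die or are transplanted before bilirubin normalises. It is worded for all survival analyses. Carried over to infection, it would treat a child who dies as never infected. The text is written about bilirubin and does not establish that this is intended, but it should be excluded explicitly. No choice of test removes the historical-control bias that the plan already acknowledges for line infections.

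**What to change.** In both the safety and the efficacy analysis sections, name one between-group method for infection rates:

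- Negative binomial regression of the infection count, or Poisson regression with robust small-sample errors, with the log of PN time at risk as offset. Report a rate ratio with its confidence interval, adjusted for the planned baseline covariates as far as the number of infections allows. Do not use plain Poisson.
- A recurrent-event Cox model with robust variance is an acceptable alternative if the team wishes to keep the named method.
- Keep time to first infection as a supporting display. Do not use Fisher's test for infection rates.
- State that the infinite-time rule for death or transplant does not apply to infection, and that time at risk ends at death or transplant.

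The cost is a change of wording and a little extra analysis on the same data. The drawback is possible model instability if infections are few, so limit the covariates accordingly.
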